## 8 Analysis Sets and Subgroups

### 8.1 Definition of Analysis Sets

#### Screening Analysis Set (SCR)

The Screening analysis set includes all participants who signed the informed consent.

#### Dose Limiting Toxicity Analysis Set (DLT)

All participants who were administered any dose of any study intervention and meet at least 1 of the following criteria:

- Experienced at least one DLT like event confirmed by the SMC during the DLT like assessment period or for whom the composite ICE strategy led to a DLT like event, regardless of the administered number of doses of study intervention/completion in the DLT like assessment period. ICE strategy is defined as

- Discontinuation/interruption/delay of xevinapant/cisplatin treatment [REDACTED] in DLT-like assessment period) due to reasons other than treatment-related AE (composite strategy: to be considered as DLT-like event)
- [REDACTED] during the DLT-like assessment period due to reasons other than treatment-related AE (composite strategy: to be considered a DLT-like event)
- [REDACTED] of xevinapant and cisplatin during the DLT-like assessment period, regardless of the completion in the DLT-like assessment period.

#### Full Analysis Set (FAS)/Safety Analysis Set (SAF)

All participants who were administered any dose of any study intervention.

#### PK Analysis Set (PK)

All participants, who receive at least one dose of study intervention, have no relevant protocol deviations or important events affecting PK, and provide at least 1 measurable postdose concentration.

#### Analyses per Analysis Set

The following table summarizes the use of the analysis sets in the different analyses.

Analyses	Analysis Set		
	FAS/SAF	DLT	PK
DLT (tolerability)		✓	
Baseline Characteristics	✓		
Previous and Concomitant Therapies	✓		
Compliance and Exposure	✓		
Efficacy	✓		
Safety	✓		

CCI

CCI

CCI

CCI

CCI

CCI

CCI

## 10 Study Participants

The subsections in this section include specifications for reporting participant disposition and study intervention/study discontinuations. Additionally, procedures for reporting protocol deviations are provided.

### 10.1 Disposition of Participants and Discontinuations

The number and percentage of participants in each of the below disposition categories will be presented. Percentages will be presented with respect to the number of treated participants.

Total number of participants screened (i.e. participants who gave informed consent) (overall only)

Number of participants who discontinued from the study prior to study intervention overall and grouped by the main reason (e.g. the failed specific inclusion or exclusion criteria, withdrawal of consent)

Number and percentage of treated participants.

The end of study intervention status will be summarized by:

- Number and percentage of treated participants with ongoing xevinapant
- Number and percentage of treated participants with ongoing cisplatin
- Number and percentage of treated participants with ongoing carboplatin
- Number and percentage of treated participants with ongoing IMRT
- Number and percentage of participants who completed xevinapant
- Number and percentage of participants who completed cisplatin
- Number and percentage of participants who completed carboplatin
- Number and percentage of participants who completed IMRT
- Number and percentage of treated participants who discontinued the xevinapant (overall and by primary reason)

- Number and percentage of treated participants who discontinued the cisplatin (overall and by primary reason)
- Number and percentage of treated participants who discontinued the carboplatin (overall and by primary reason)
- Number and percentage of treated participants who discontinued the IMRT (overall and by primary reason)

The end of study status will be summarized by:

- Number and percentage of treated participants with ongoing any study intervention
- Number and percentage of treated participants off-treatment and in follow-up period
- Number and percentage of treated participants who completed or prematurely discontinued the study after, grouped by main reason

Additionally, the number of participants screened, and enrolled in each analysis set will be provided overall, by region (North America, Western Europe, EEA (required by EudraCT), and Rest of the world), by country within region and by site.

The number of participants treated in each analysis set will be provided.

## 10.2 Protocol Deviations / Exclusion from Analysis Sets

### 10.2.1 Important Protocol Deviations

Important protocol deviations (IPDs) are protocol deviations that might significantly affect the completeness, accuracy, and/or reliability of the study data or that might significantly affect a participant's rights, safety, or well-being.

Important protocol deviations include:

- Participants enrolled and dosed on the study who did not satisfy enrolment criteria
- Participants that develop withdrawal criteria whilst on the study but are not withdrawn
- Participants that receive the wrong study intervention or an incorrect dose
- Participants that receive an excluded concomitant medication
- Failure to collect data necessary to interpret primary endpoints
- Failure to collect necessary key safety data
- Deviation from Good Clinical Practice (GCP)
- Any other protocol deviation that might significantly affect the completeness, accuracy, and/or reliability of the study data or that might significantly affect a participant's rights, safety, or well-being.

Important protocol deviations will be identified for all participants by either site monitoring, medical review processes or programming and confirmed prior to or at the Data Review Meeting at the latest.

Any protocol deviation is documented in SDTM datasets whether identified through site monitoring, medical review or programming. The management of protocol deviations is outside of this IAP document.

Important protocol deviations or important events that might have an effect on PK include, but may not be limited to the following:

- Sample processing errors that may lead to inaccurate bioanalytical results
- Inaccurate dosing or dosing errors (e.g., dose administration delayed, dose change or missed doses), when dosing information is available
- Pre-dose or trough sample collected after the actual dosing
- Concomitant medications and dietary or herbal supplements that are known potent inhibitors or inducers of P-glycoprotein (Table 13 of protocol).

Should one or more of these events be available at the Data Review Meeting, its implication for PK evaluation will be discussed and agreed amongst relevant study team members (e.g. Sponsor Clinical Pharmacology/Biostatistics/Clinical Pharmacokinetics & Pharmacodynamics team representative). Appropriate action will be taken such as flagging individual values to be excluded from analysis.

A frequency table as well as a listing of important protocol deviations, will be provided based on the FAS/SAF.

### **10.2.2 Reasons Leading to the Exclusion from an Analysis Set**

All criteria/reasons leading to the exclusion of a participant from an Analysis Set should be summarized and listed (see Section 10.1).

If participants are excluded from the DLT, PK Analysis Set, the reasons for exclusion will be listed.

## **11 Demographics and Other Baseline Characteristics**

If not stated otherwise, the following analyses will be performed based on the FAS/SAF.

### **11.1 Demographics**

Demographic characteristics and physical measurements will be summarized descriptively using the following information from the Screening/Baseline Visit eCRF pages.

The following demographic characteristics will be included:

- Sex:

- male
- female
- undifferentiated
- Race:
  - American Indian or Alaska Native
  - Asian
  - Black or African American
  - Native Hawaiian
  - Other Pacific Islander
  - White
  - More than one race
  - Other
  - Not collected at this site
- Ethnicity:
  - Hispanic or Latino
  - Not Hispanic or Latino
- Age (years)
- Age categories:
  - < 65 years,
  - ≥ 65 years
    - 65-74,
    - 75-84,
    - ≥85 years
- Pooled Region:
  - North America
  - Europe
  - Asia
  - Rest of the World
- Geographic Region:
  - North America
  - Latin America
  - Western Europe

- Eastern Europe
  - Middle East
  - Australia
  - Asia
- Weight (kg)
- Height (cm)
- BMI (kg/m^2) at Baseline
- BSA (m^2) at Baseline
- ECOG Performance status (0,1,2,3,4)

**Specifications for computation:**

$$\text{BSA [m}^2\text{]} = \sqrt{\frac{\text{height[cm]} \times \text{weight[kg]}}{3600}}$$

$$\text{BMI [kg/m}^2\text{]} = \frac{\text{weight [kg]}}{\text{height[cm]}^2} \times 10000$$

Site codes will be used for the determination of the participant's geographic region.

**11.2 Medical History**

The medical history will be summarized from the "Medical History" eCRF page, using the most recent MedDRA version at time of database lock, preferred term as event category and system organ class (SOC) body term as Body System category. Each participant will be counted only once within each PT or SOC.

Medical history will be displayed in terms of frequency tables: ordered by primary SOC and PT in alphabetical order. All medical history data will be listed.

**11.3 Other Baseline Characteristics**

Information on other baseline characteristics collected at baseline will be summarized. Summary statistics will be presented for:

- Disease History:
  - Site of primary tumor
  - Time since initial cancer diagnosis (months)
  - Histopathological grade
  - Pathological stage (derived from the TNM values) and TNM classification at study entry
- Nicotine usage:
  - Nicotine usage (never smoker, current smoker, former smoker)

- Nicotine usage type (cigarettes, cigars, pipes, chewing tobacco, nicotine gum, e-cigarettes or vapor)
  - Nicotine exposure (pack-years)
  - Nicotine exposure time (years)
  - Years since quitting
- Alcohol consumption:
  - Alcohol consumption (Yes/No)
  - Alcohol consumption (units per week)
- ECOG performance status
- Height, Weight, Body Surface Area, and Body Mass Index
- HPV status at screening

#### Specifications for nicotine usage computation:

Nicotine usage will be derived using information about the use of nicotine products that can be smoked: cigarettes, cigars, pipes.

The information collected about products that are smoked will be used to derive the smoking status for each participant:

- Current Smoker: a participant is a current smoker if at least one smoked product was answered “Current” (missing information about one or more smoked products is allowed);
- Former Smoker: a participant is a former smoker if he/she is not a current smoker and at least one smoked product was answered “Former” (missing information about one or more smoking options is allowed);
- Never Smoker: a participant is considered to have never smoked if all the smoking options were answered “Never”.
- Missing: in case the information is missing for one or more of these smoking options and the participant cannot be classified as current or former smoker, the smoking status should be “Missing”, even though all the remaining options were answered “Never”.

#### Nicotine history computation:

- Chewing tobacco, nicotine gum and e-cigarette are not taken into account for nicotine exposure calculation
- Cigarette equivalents are calculated as follow: 1 cigar is regarded equivalent to 5 cigarettes and 1 pipe is regarded equivalent to 3 cigarettes
- Duration of smoking (years):
  - (end date of smoking – start date of smoking +1)/ 365.25

- Pack-year:
  - Calculate cigarette equivalents per day using the conversion factors given above
  - Convert to packs per day where 20 cigarettes are regarded as 1 pack
  - Pack-year=packs per day\*duration of smoking (years)

**Specifications for alcohol consumption computation:**

- Units per day are calculated as follow: 360ml or 12oz of beer is regarded equivalent to 1 unit, 150ml or 5oz of wine is regarded equivalent to 1 unit and 45ml or 1.5oz of spirits is regarded equivalent to 1 unit
- units per week:
  - Calculate units per day equivalents using the conversion factors given below
  - Convert to units per week \*7

## 12

## Previous or Concomitant Therapies/Procedures

The following analyses will be performed based on the SAF.

**Concomitant medications** are medications, other than study intervention, which are taken by participants any time during the on-treatment period, see Section 9.8.

**Previous medications** are medications, other than study intervention, which started before first administration of study interventions.

A medication may be classified as both concomitant and previous. The respective flags will be derived based on start and end date.

Concomitant and previous medication each will be summarized by number and percentage of participants from the “Previous and Concomitant medication and/or Therapies” eCRF. Preferred term within ATC Classification code level 2 will be tabulated as given from the WHO-DD dictionary most current version.

If any previous or concomitant medication is classified into multiple ATC classes, the medication will be summarized separately under each of these ATC classes

The summary tables will be sorted by decreasing frequency of drug class and decreasing frequency of preferred term in a given drug class. In case of equal frequency regarding ATC classification level 2 or preferred term, alphabetical order will be used.

In case any specific medication does not have an ATC classification level 2 coded term, it will be summarized under “Unavailable ATC classification” category. Each participant will only be counted once, even if he/she received the same medication at different times.

All concomitant procedures will be listed.

### Subsequent anti-cancer therapy

Anti-cancer therapy after end of study intervention will be summarized according to the respective CRF page. Treatments will be categorized by means of coding and medical review. The same approach as for concomitant medications will be applied based on ATC level 2 and preferred term.

Number and percentage of participants with any anti-cancer post study treatment and by type (anticancer treatment, radiotherapy, surgery) will be presented.

Summary statistics will be created for best response across all post study treatments (as indicated on “Follow up treatment” page). For participants who received more than one anti-cancer drug therapy after discontinuation of study intervention, the best overall response among all anti-cancer drug therapies will be summarized.

## 13 Study Intervention: Compliance and Exposure

The following analyses will be performed based on SAF.

All dosing calculations and summaries will be based on “Study Drug Administration” CRFs pages.

If the total dose is missing, the protocol defined dose of each study intervention will be used.

No imputation of missing start dates of study interventions will be done.

In case the last date of study intervention is incomplete the date of last study intervention administration will be taken from the End of Treatment page.

For Cycle X, actual cycle start date for each participant is:

- the earliest start date of dosing in the Cycle X Day 1 visit eCRF exposure page, if the participant received any study intervention on that visit (i.e., any study intervention with dose>0 at that visit)
- the first day of assessments in the Cycle X Day 1 visit, if the participant did not receive study intervention on that visit (i.e., all study interventions had dose=0 at that visit). Use start date in the exposure page if available; if start date is not available then use date of collection of vital signs (assuming vital signs are the first assessment of the cycle on Cycle X Day 1 visit).

Actual cycle end date for each participant is:

- for all cycles X except the last cycle, actual cycle end date = actual cycle (X+1) start date – 1 day;
- for the last cycle, actual cycle end date = actual cycle start date + intended cycle duration (in days) – 1 day

Cycle duration (weeks) = (actual cycle end date – actual cycle start date + 1)/7

When summarizing exposure for each study intervention, only cycles with non-zero dose of study intervention of at least one of the study interventions should be included.

A dose is regarded to be administered, if the actual dose received is > 0, or the duration of the infusion is > 0, or the start date or end date is not missing.

**Xevinapant Cumulative dose (mg)** overall is the sum of the actual doses of study intervention received overall. Actual dose per day is collected using mL on eCRF. This dose will be converted to mg as:

$$\text{Actual dose (mg)} = \text{Actual dose (mL)} * 20 \text{ (mg/mL)}$$

**Xevinapant Dose intensity (mg/day)** is defined as the cumulative dose of xevinapant by the cycle duration in days as:

$$\text{dose intensity} = \left( \frac{\text{cumulative dose}}{(\text{planned dosing days per cycle (14 days)}) * \text{exposure duration (cycles)}} \right)$$

**Cisplatin/carboplatin Cumulative dose (mg/m^2 or AUC)** overall is the sum of the actual doses of study intervention received overall, respectively.

**Cisplatin/carboplatin Dose intensity (mg/m^2/day or AUC/day)** is defined as the cumulative dose of cisplatin/carboplatin by the exposure duration in days as:

$$\text{dose intensity} = \left( \frac{\text{cumulative dose}}{(\text{planned dosing days per week (1 day)}) * \text{exposure duration (weeks)}} \right)$$

**IMRT Cumulative dose (Gy)** overall is the sum of the actual doses of study intervention received overall. If a IMRT dose modification will occur PTV1 new reported value will be used for the calculation.

**IMRT Dose intensity (Gy/day)** is defined as the cumulative dose of IMRT by the exposure duration in days as:

$$\text{dose intensity} = \left( \frac{\text{cumulative dose}}{(\text{planned dosing days per week (5 days)}) * \text{exposure duration (weeks)}} \right)$$

**Relative dose intensity (%)** is defined as the actual dose intensity divided by the planned dose intensity during the study and expressed in percentage:

$$\text{relative dose intensity} = \left( \frac{\text{dose intensity}}{\text{planned dose}} \right) * 100$$

Where the planned dose is:

- Xevinapant: **CCI** mg/day
- Cisplatin: **cci** mg/m^2/day
- Carboplatin: AUC2/day
- IMRT: 70 Gy/day

The summary of study intervention exposure will include the following information:

- Total duration of xevinapant, cisplatin, carboplatin and IMRT (weeks) and by categories of  $\leq$  3 weeks,  $> 3 - 6$  weeks,  $> 6 - 9$  weeks,  $> 9 - 12$  weeks,  $> 12 - 15$  weeks,  $> 15 - 18$  weeks
- Number of IMRT Fractions
- Total number of cycles received of xevinapant, cisplatin, carboplatin and IMRT
- Cumulative dose of xevinapant, cisplatin, carboplatin and IMRT
- Dose intensity of xevinapant, cisplatin, carboplatin and IMRT
- Relative dose intensity (%) of xevinapant, cisplatin, carboplatin and IMRT
- Dose reduction of xevinapant, cisplatin, carboplatin and IMRT per time period (overall and by reason)
- Missed doses of xevinapant, cisplatin, carboplatin and IMRT per time period
- Discontinuation of xevinapant, cisplatin, carboplatin and IMRT per time period (overall and by reason)
- A listing will be provided for all administrations of participants for the primary analysis only.

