6.5.1.2 Dose Modification, Interruption, and Discontinuation of Xevinapant Treatment

For participants who do not tolerate the study intervention, adjustments to the study intervention dose are permitted to allow the participant to continue on-study intervention according to the guidelines below.

The guidelines for xevinapant dose modifications for toxicities considered at least possibly related to study intervention are outlined in Table 7 and Table 8, for combination therapy and monotherapy, respectively. These dose modifications are recommendations unless otherwise specified as mandatory. All dose modifications should be based on the worst preceding toxicity (NCI-CTCAE v5.0). Additionally, nontreatment-related events, or unexpected toxicities may require interruption of study intervention at the discretion of the Investigator.

In case a dose reduction is necessary, the study intervention will be administered as follows:
For each participant, a maximum of 2 dose reductions of xevinapant will be allowed during the study.

The volume of the oral solution equivalent to each dose level is the following:

- Planned dose (Level 0): CCI corresponds to CCI mg/day of xevinapant
- Dose Level 1: CCI corresponds to CCI mg/day of xevinapant
- Dose Level 2: CCI corresponds to CCI mg/day of xevinapant

General rules for xevinapant administration throughout the treatment period (C1 to C6) are:

[figure not shown]
- The number of treatment days with xevinapant intake should not exceed 14 days per cycle.
- In case of tolerability issues, up to 2 sequential xevinapant dose reductions of CCI mg/day (CCI of oral solution) per step will be allowed, down to a minimum dose of CCI mg

CCI [REDACTED] of oral solution). If further dose reduction is required, the participant must be permanently discontinued from xevinapant administration (other ongoing treatments can continue, see Sections 6.5.2 and 6.5.3).

[figure not shown]
- If the onset of several toxicities leads to conflicting recommendations as described in Table 7 the most conservative dose adjustment among all toxicities presented must be followed.
- **No re-escalation** of xevinapant dose after dose reduction will be allowed during the study. Once xevinapant dose has been reduced, participant will keep receiving the same dose until the EOT, or until further dose reduction or permanent treatment discontinuation, if required due to tolerability issues.

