6.5.2.1 Dose Modification, Interruption, and Discontinuation of Chemotherapy

Permitted cisplatin dose levels:

- Planned dose (level 0): corresponds to cisplatin **CCI** mg/m²
- Dose level - 1: corresponds to cisplatin **CCI** mg/m² **CCI**
- Dose level - 2: corresponds to cisplatin **CCI** mg/m² **CCI**

For participants switching to carboplatin: carboplatin AUC = 2 mg·min/mL is allowed.

Please refer to [Table 7](#) for instructions on dose modifications, interruption, discontinuation of chemotherapy, and potential switch to carboplatin in case of toxicity suspected to be related to study intervention.

Toxicity related to chemotherapy administration includes but is not limited to nausea, vomiting, renal toxicity (with an elevation of blood urea nitrogen and creatinine and impairment of endogenous creatinine clearance, as well as renal tubular damage, which appears to be transient), peripheral neuropathy, ototoxicity (with hearing loss that initially is in the high-frequency range, as well as tinnitus), and hyperuricemia. Much more severe and prolonged toxicity has been observed in participants with abnormal or obstructed urinary excretory tracts. Myelosuppression, often with delayed anemia, is expected.

Chemotherapy dose adjustments at the start of a cycle should be based on the nadir of hematologic counts or maximum nonhematologic toxicity from the previous treatment cycle. Chemotherapy infusion may be delayed to allow for sufficient recovery time.

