9.3 Analysis Sets

The analysis sets are specified below.

Table 16 Analysis Set

Analysis Set	Description
SCR	All participants who provided informed consent, regardless of the study intervention status in the study.

Analysis Set	Description
DLT	All participants who were administered any dose of any study intervention and meet at least 1 of the following criteria: 
Experienced at least one DLT like event confirmed by the SMC during the DLT like assessment period or for whom the composite ICE strategy led to a DLT like event, regardless of the administered number of doses of study intervention/completion in the DLT like assessment period.Received at least 60% of the planned cumulative dose of xevinapant and cisplatin during the DLT-like assessment period, regardless of the completion in the DLT-like assessment period.
FAS/SAF	All participants who were administered any dose of any study intervention.
PK	All participants, who receive at least 1 dose of xevinapant, have no relevant protocol deviations or important events affecting PK, and provide at least 1 measurable postdose concentration.

DLT=dose-limiting toxicity, FAS=full analysis set, PK=pharmacokinetic, SAF=safety, SCR=screening.

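### SAP Section 13 fills a missing dose amount with the protocol dose and shows no exception for participants already reduced, which biases exposure and relative dose intensity upward

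*SAP*

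**What the plan says.** SAP Section 13 governs exposure: "The following analyses will be performed based on SAF". Its data source is broad: "All dosing calculations and summaries will be based on" the study drug administration CRF pages. For a missing amount it says: "If the total dose is missing, the protocol defined dose of each study intervention will be used". A dose counts as administered if the amount is above zero, the infusion duration is above zero, "or the start date or end date is not missing". A dated record with no amount therefore counts as given and falls under the imputation rule.

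The protocol provides several dose levels. Section 6.5.1.2 says "For each participant, a maximum of 2 dose reductions of xevinapant will be allowed during the study" and that no re-escalation "of xevinapant dose after dose reduction will be allowed during the study". Section 6.5.2.1 lists, under "Permitted cisplatin dose levels", the planned level and two lower ones. Section 6.5.1.2 requires each modification and interruption to be recorded on the eCRF with its reason. For IMRT, SAP Section 13 takes the newly reported value after a modification. It shows no such rule for xevinapant or cisplatin.

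SAP Section 7.1, added in version 2.0, reduces the scope to a 6-patient SMC analysis and a synoptic CSR. It keeps cumulative dose, dose intensity and RDI.

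**The concern.** A participant's current level can be read from the eCRF, yet the rule points to the protocol dose. The only planned dose that SAP Section 13 lists for each drug is a single fixed value. After a reduction, the imputed amount is then higher than any dose the participant could have been given under the no-re-escalation rule. The error runs one way: it makes the combination look better delivered than it was, in a study whose question is tolerability.

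A second consequence is conditional. A participant without a DLT-like event enters the DLT analysis set by this route (Protocol 9.3): "Received at least 60% of the planned cumulative dose of xevinapant and cisplatin during the DLT-like assessment period". The estimand counts more than 40% of planned dose missed for other reasons as a DLT-like event. Protocol 8.2.5.1 counts less than 60% in a cycle, due to a treatment-related AE, as one. All three are numerical dose checks. If they were programmed from Section 13 doses, an inflated amount could move a participant across the line.

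**Working it through.** The plan states no figure for this point, so there is nothing to reproduce first.

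**Inputs**
- Xevinapant: 14 doses per cycle, 6 cycles, so 84 doses (Protocol 6.5.1).
- Cisplatin: 7 weekly doses, 3 in each of Cycles 1 and 2 and 1 in Cycle 3 (Protocol 4.1).
- In the 5-week DLT-like period: 5 cisplatin doses (3 in Cycle 1, 2 in Cycle 2).
- r = reduced level as a fraction of level 0. The levels are redacted, so r = 0.75 is an assumption, with range 0.9 to 0.5.
- m = administered doses at the reduced level whose amount is missing.

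**RDI**

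Each imputed record adds (1 − r) of a level-0 dose:
- Xevinapant, six cycles: (1 − r)/84. At r = 0.75 this is 0.25/84 = 0.30 points; at 0.9, 0.12; at 0.5, 0.60.
- Cisplatin, seven doses: (1 − r)/7. At r = 0.75 this is 0.25/7 = 3.6 points; at 0.9, 1.4; at 0.5, 7.1.

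Xevinapant reduced to 0.75 from Cycle 2, all doses taken:
- True: (14 + 70 × 0.75)/84 = 79.2%.
- m = 7: (14 + 63 × 0.75 + 7)/84 = 81.25%.
- m = 14: (14 + 56 × 0.75 + 14)/84 = 83.3%.

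Cisplatin with three doses at level 0 and four at 0.75:
- True: (3 + 4 × 0.75)/7 = 85.7%.
- One amount missing: (3 + 3 × 0.75 + 1)/7 = 89.3%.

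**Per-cycle share of planned dose, only if programmed from these doses**

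Protocol 8.2.5.1 treats a dose reduced at the start of the next cycle as the new planned dose, so the denominator is rebased. With n scheduled doses and k recorded at level r, the share is (k·r + m)/(n·r) under the SAP rule and (k + m)/n in truth.

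Xevinapant, 8 of 14 doses taken, true share 8/14 = 57.1%:

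| r | m | SAP rule |
|---|---|---|
| 0.5 | 1 | (7 × 0.5 + 1)/7 = 64.3% |
| 0.75 | 2 | (6 × 0.75 + 2)/10.5 = 61.9% |
| 0.8 | 2 | (6 × 0.8 + 2)/11.2 = 60.7% |
| 0.9 | 4 | (4 × 0.9 + 4)/12.6 = 60.3% |

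Cisplatin, 1 of 3 doses given and its amount missing: true share 33.3%; SAP rule 1/(3r), which is 44.4% at r = 0.75 and reaches 60% only if r ≤ 0.556.

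**5-week share, same condition**

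The text does not say whether rebasing applies to the period checks, so both denominators are shown. Cisplatin, r = 0.75 in Cycle 2, one amount missing:
- Level-0 denominator, two doses in Cycle 1 and one in Cycle 2: true (2 + 0.75)/5 = 55%; SAP rule (2 + 1)/5 = 60%.
- Rebased denominator 3 + 2 × 0.75 = 4.5, one dose in Cycle 1 and two in Cycle 2: true (1 + 1.5)/4.5 = 55.6%; SAP rule (1 + 0.75 + 1)/4.5 = 61.1%.

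**If the dose was not taken**

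Imputing the current level then hides the gap as well: one such xevinapant record turns 8/14 = 57.1% into 9/14 = 64.3%. The fix therefore needs a zero branch as well as the current-level branch.

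**The case against.** **The DLT link.** A reader might infer that the rule hides the shortfall that defines a DLT-like event. The documents do not support that as a statement of fact. Section 13 is an exposure section on the SAF. DLT-like events are recorded by the site (Protocol Appendix 7) and confirmed by the SMC (8.2.5.1), and the SMC outputs use DLTs as per investigator (SAP Appendix 1). The below-60% rule is one criterion among several and needs a treatment-related AE. SAP Sections 9.11 (imputation) and 9.14 (DLT-like period) appear in the contents but are redacted, so a separate rule may exist. Section 7.1 lists no DLT-like event output. This objection stands, and the link is kept only as a condition. It does not dispose of the numerical 60% and 40% checks, which investigator reporting and SMC confirmation of events do not settle. Section 7.1 still lists an analysis-set table, and SAP Section 15.1 is not marked as dropped in the way Sections 14 and 16 are.

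**Untaken doses.** A reader might also infer that skipped home doses become full ones, so that 8 of 14 taken (57%) is reported as 100%. That needs six records carrying a date but no amount, with none recorded as skipped. The rule covers a missing amount, not every missed dose. Section 13 recognises a recorded dose of 0, and the protocol requires skipped doses in the diary and deviations in the CRF. Missed doses are also not among the outputs kept in Section 7.1.

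**Size.** The per-record effect on xevinapant RDI is small. The cisplatin effect is larger, but clinic doses are supervised and checked by a second person (Protocol 6.4), so missing amounts should be few. This is fair and limits the weight of the point.

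**Wording.** The phrase used for the imputed dose could be read as the protocol's dose for the participant's current level. The text does not say so, and the IMRT sentence shows that the SAP states such a rule when it means one.

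**Conclusion.** The point holds for the exposure outputs. As written, the imputation rule makes no visible allowance for reduced doses and biases cumulative dose, dose intensity and RDI upward. At r = 0.75 the bias is about 0.30 points per imputed record for six-cycle xevinapant RDI and 3.6 points for seven-dose cisplatin RDI, with the ranges shown above for r from 0.9 to 0.5.

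This assumes that the imputed dose is level 0, that nothing in the redacted SAP Section 9 overrides it, and that some reduced participants have dated records with no amount. The number of such records is unknown; with none, there is no effect.

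Misclassification on the 60% or 40% checks is possible near the threshold, but only if those checks use Section 13 doses. The visible text does not establish this.

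**What to change.** Replace the sentence in SAP Section 13 with a rule along these lines:
- Where a record shows administration but the amount is missing, impute the participant's last recorded dose level for that drug.
- Where the eCRF shows that the dose was not taken, use 0.
- Otherwise leave the amount missing.
- Do not use imputed amounts for the 60% received, below-60% or above-40%-missed checks.
- Report the number of imputed records by drug.

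The cost is a short SAP edit and a little programming, using data already on the eCRF. RDI may look slightly lower. SAP version 2.0 (14 March 2025) postdates the database lock that it cites (20 September 2024). If the exposure tables already exist, a count of imputed records and a sensitivity table under the new rule would suffice. This is a data-handling change and alters no dose or treatment rule.
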